### **3.2.2 Treatment Area**

The treatment area with the IMP is defined as follows.

- The treatment area selected at baseline examination will be affected area determined at baseline examination (see “3.7.4.6 Affected BSA”).
- After the baseline examination, when the affected area has expanded or a new affected area is detected, the expanded or newly affected area will also be included in the treatment area.
- Even when the affected area is relieved, the IMP administration should be continued there as the treatment area.

The investigator or subinvestigator will instruct the subject regarding the method of administration by specifying the treatment area (%) and the amount of administration (g) for each treatment area using the human body drawing (Appendix 4 for children aged 8 to 14 years old and Appendix 5 for children aged 2 to 7 years old), and will give the human body drawing (copy) to the subject or the subject’s legal guardian. The investigator or subinvestigator will record the treatment area (%) of the 4 body regions (face, neck, and head; upper limbs; trunk; and lower limbs) in the source document and case report form (CRF).

The method of IMP administration is specified in the separate procedure for IMP administration.

### **3.3 Trial Population**

#### **3.3.1 Number of Subjects and Description of Population**

The target population of this trial is pediatric patients with AD with an IGA score of 2 (mild) or 3 (moderate). Subjects will be included in the trial to reach the target number of 60 subjects for IMP administration (at least 8 subjects aged 2 to 6 years old). Any withdrawals will not be supplemented.

#### **3.3.2 Subject Selection and Numbering**

For the subjects whose legal guardians have provided informed consent, the investigator or subinvestigator will assign the subject identification code and subject number (3 digit number of site ID + S + 5 digit serial number starting from 00001).

### **3.4 Eligibility Criteria**

#### **3.4.1 Informed Consent**

Freely given written informed consent will be obtained from the subjects' legal guardians (guardians or legal representatives, as applicable by law) instead of the subjects. If possible, assent (consent not bound by the legal restrictions obtained from pediatric subjects) will be obtained from the subjects participating in the trial. A signed informed consent form will be retained as a document, and a signed assent form will also be retained as a document. The explanatory document, informed consent form, and assent form will be approved by the same institutional review board (IRB) responsible for approval of this protocol.

Each explanatory document and informed consent form should include the elements required by the International Conference on Harmonization (ICH) Guidelines for Good Clinical Practice (GCP) and local regulatory requirements.

The investigator or subinvestigator may discuss the availability of the trial and the possibility for entry with a potential subject and subject's legal guardian before obtaining consent. However, written informed consent must be obtained from the subject's legal guardian prior to the initiation of any procedures that are performed solely for the purpose of determining eligibility for this trial, including withdrawal from current medications.

The potential subject and subject's legal guardian can refuse to participate in or withdraw from the trial at any time without any justifiable reason. The refusal or withdrawal by the potential subject and subject's legal guardian will not affect any future treatments.

Once the appropriate essential information and a full explanation in layman's language appropriate for the potential subject's age have been provided by the investigator or subinvestigator, the IRB-approved informed consent form will be personally signed and dated by the subject's legal guardian and the person obtaining informed consent (investigator or subinvestigator). When assent is also obtained from the subject, the assent form will be personally signed and dated by the subject (if possible) and the person obtaining informed consent (investigator or subinvestigator), in the same manner. When a supplemental explanation is given by a clinical trial associate, the clinical trial associate will also sign and date the form. The subject's legal guardian will be given the explanatory document and copies of the signed informed consent form and assent form, and the originals will be kept by the investigator or subinvestigator.

If an amendment to the protocol substantially increases or alters the trial procedures, the subject's legal guardian may be asked for an additional consent and to again sign the form.

### 3.4.2 Inclusion Criteria

Subjects are required to meet the following inclusion criteria #1 through #5 in Table 3.4.2-1 at the screening examination, and #6 and #7 at the screening examination and the baseline examination.

Table 3.4.2-1 Inclusion Criteria	
1	Sex: Either male or female
2	Hospitalization status: Outpatient
3	Age: 2 to 14 years, inclusive (at time of obtaining informed consent)
4	Diagnosis of AD based on the criteria of Hanifin and Rajka  (Appendix 1)
5	Subjects whose legal guardian is able to provide informed consent prior to participation in the trial
6	AD affecting $\geq 5\%$ to $\leq 40\%$ of BSA
7	IGA score of 2 (mild) or 3 (moderate)

#### [Rationale for Inclusion Criteria]

- 1) AD occurs in both males and females.
- 2) Most patients to be included in this trial are outpatients.
- 3) The objective of this study is to evaluate the safety and efficacy of the OPA-15406 ointment in pediatric patients. In consideration of the standard age classification in ICH-E11 and the package insert, children aged 2 to 14 years old are selected. In the toxicity study in juvenile animals, suppressed weight increase and reductions in food intake and grip strength were observed in female rats with 1% or 3% ointment. However, these changes were not developmental toxicity specific to juvenile rats, and there was no difference in the toxicity threshold between adult and juvenile rats. In the phase 1 trial in Japanese healthy adult subjects (271-14-001) and in the phase 2 trial in patients aged 10 years and older outside Japan (271-12-205), no particular safety concerns were raised.
- 4) The criteria of Hanifin and Rajka have been most commonly used worldwide and have the same major diagnostic criteria as those of the Japanese Dermatological Association; therefore, the criteria can be used also in Japan without problems.
- 5) In consideration of ethical issues concerning patients who are minors.
- 6), 7) To appropriately evaluate the efficacy of the IMP on the target disease.

### 3.4.3 Exclusion Criteria

Subjects will be excluded if they meet any of the exclusion criteria in Table 3.4.3-1 at the screening examination and the baseline examination.

1	Subjects who have an AD or contact dermatitis flare-up defined as a sudden intensification of AD, within 28 days prior to the baseline examination
2	Subjects who have a concurrent or history of skin disease other than AD (eg, acne, psoriasis, Netherton's syndrome, ichthyosis, graft versus host disease, etc) and who are judged inappropriate for assessment of AD in the present trial
3	Subjects who have an active viral skin infection (eg, herpes simplex, herpes zoster, chicken pox) or a clinical sign of any of these
4	Subjects who have a concurrent or history of malignancy
5	Subjects with a history of recurrent bacterial infection resulting in hospitalization or requiring intravenous antibiotic treatment
6	Subjects with a clinically significant complication or history of any of the following disorders that the investigator or subinvestigator judges would prevent safe conduct of the trial or impact efficacy assessments: 
 
• Cardiac disease (eg, rheumatic fever or heart valve replacement)
 
• Endocrinologic disease (eg, severe or uncontrolled diabetes)
 
• Pulmonary disease
 
• Neurologic disease
 
• Psychiatric disease
 
• Hepatic disease (eg, hepatitis B, hepatitis C)
 
• Renal disease
 
• Hematologic disease
 
• Immunologic or immunocompromised disease (eg, lymphoma, acquired immunodeficiency syndrome, Wiskott-Aldrich syndrome, carriers of human immunodeficiency virus [HIV] antibodies)
 
• Other major disease (eg, systemic fungal infection) or other severe uncontrolled condition (eg, drug or alcohol abuse) judged by the investigator or subinvestigator to pose a health risk to the subject or to have the potential to impact trial assessment
 

7	Based on the laboratory test results at the screening examination, subjects for whom it is deemed by the investigator or subinvestigator that the trial cannot be conducted safely.
8	Subjects who are judged by the investigator or subinvestigator to have a clinically significant electrocardiogram (ECG) findings at the screening examination. (For children aged 2 - 6 years old, a 12-lead ECG will be recorded,

Table 3.4.3-1 Exclusion Criteria	
	as much as possible.)
9	Subjects who are judged by the investigator or subinvestigator to have a clinically abnormal blood pressure or pulse rate at the screening examination
10	Subjects who are judged by the investigator or subinvestigator to be problematic in withdrawing blood
11	Subjects who are unable to stop using topical corticosteroids, topical immunomodulators, topical retinoids and topical antihistamine from 7 days prior to the baseline examination until the Week 4 examination. Low or medium potency corticosteroids in the Guidelines for Management of Atopic Dermatitis  may be used until 4 days prior to the baseline examination in the judgment of the investigator or subinvestigator for the gradual decrease in the screening period before stopping.
12	Subjects who are unable to stop using systemic corticosteroids, systemic immunomodulators, systemic antimetabolites, systemic retinoids, and biologics from 28 days prior to the baseline examination until the Week 4 examination. Intra-ocular, intra-nasal and intra-auricular or inhaled corticosteroids may be considered if, in the opinion of the investigator or subinvestigator, their use will not impact assessment of the affected area.
13	Subjects who are unable to stop treatment with ultraviolet A , narrowband ultraviolet B, and ultraviolet B from 28 days prior to the baseline examination until the Week 4 examination
14	Subjects who are unable to continue in the trial without changing the dosage and administration of systemic antihistamines, sodium cromoglicate, tranilast, or suplatast tosilate from 7 days prior to the baseline examination until the Week 4 examination. Intra-ocular, intra-nasal, or inhalant formulations may be considered if, in the opinion of the investigator or subinvestigator, their use will not impact the assessment of the affected area.
15	Subjects with known hypersensitivity (including history) to any drugs (prescription, OTC, etc) or any ingredient of OPA-15406 ointment (eg, white petrolatum, mineral oil, paraffin, white wax, or propylene carbonate)
16	Subjects with known plans to receive any of the prohibited concomitant drugs or therapies during the trial period
17	Subjects who have used any other investigational drug within 4 months prior to the baseline examination or who are scheduled to participate in any other clinical trial during the trial period
18	Subjects who have never been treated with a prescription medication for AD or who are satisfied with their current AD treatment regimen
19	Female subjects aged 7 to 14 years old who are pregnant or suspected of being pregnant, or who cannot agree to abstain from any actions that have the possibility of resulting in pregnancy
20	Subjects who are judged by the investigator or subinvestigator to be inappropriate to participate in the trial for any other reason

[Rationale for Exclusion Criteria]

- 1), 11)-13) Due to a possible impact on the efficacy evaluation of the IMP.
- 2), 6), and 16) Due to a possible impact on the safety and efficacy evaluation of the IMP.
- 3)-5) In consideration of safety.
- 7)-10) In consideration of safety.
- 14) Due to a possible impact on the efficacy evaluation of the IMP and in consideration of safety.
- 15) In consideration of safety.
- 17) In reference to the “Criteria for Period to Avoid Participation in Clinical Studies” of the Japan Association of Contract Institutes for Clinical Pharmacology.
- 18) To exclude patients who are not in need of treatment and to prevent registering patients who are satisfied with their current treatment, because trials have aspects of research.
- 19) To prevent unknown consequences of the IMP in pregnant women, fetuses, or infants, and in consideration of safety.
- 20) To allow the investigator or subinvestigator to judge in consideration of other factors.

### **3.5 Endpoints**

#### **3.5.1 Primary Endpoint**

The number and percentage of subjects experiencing AEs

[Rationale]

To properly evaluate the safety of OPA-15406.

#### **3.5.2 Secondary Endpoints**

IGA, Eczema Area and Severity Index (EASI), Visual Analogue Scale (VAS) for pruritus (only for patients aged 7 - 14 years old), Visual Rating Scale (VRS) for pruritus (only for patients aged 7 - 14 years old), Patient-Oriented Eczema Measure (POEM), and affected BSA

[Rationale]

IGA is selected because it is one of the reliable indicators to assess the severity of AD symptoms and to determine the efficacy of IMP. IGA is evaluated based on the severity of overall symptoms (eg, erythema, infiltration, papules, effusion, and scab formation) at administration sites and does not include other factors (eg, excoriation, lichenification, severity at each part, subjective symptoms, and affected BSA). For this reason, EASI, VAS for pruritus, VRS for pruritus, POEM, and affected BSA are also established to evaluate the efficacy from multiple points of view.

Plasma concentration of OPA-15406 (the trough concentration at Week 1 and Week 4)  
[Rationale]

To determine the internal exposure to OPA-15406 in pediatric AD patients.

### **3.6 Measures to Minimize/Avoid Bias**

This trial is a randomized, double-blind trial.

The IMP allocation manager will prepare a master “random allocation table” hereinafter, “randomization table”) and conduct IMP coding according to the operating procedures for randomization. Also, the IMP allocation manager will prepare an emergency code list for use in emergencies such as the occurrence of a serious adverse event.

The investigator, subinvestigator, and subjects are blind to the IMP randomization code. Except for some designated personnel, the sponsor’s trial staff, including the personnel of contract research organizations, are also unable to access the IMP randomization code during the trial period.

Prior to the trial start and unblinding, the IMP allocation manager will confirm that the IMPs are indistinguishable. The randomization table is sealed by the IMP allocation manager just after completion of IMP randomization and it is kept under strict control until unblinding after fixation of all CRFs and the database.

The emergency code list will be kept under strict control by the registration system until the end of the trial. If a medical emergency occurs in a subject and knowledge of his or her IMP randomization code is considered important for treatment, the emergency code will be broken according to the “5.7 Procedure for Breaking the Blind.”

When IMPs are recovered by the sponsor prior to unblinding, they are to be recovered sealed by the IMP manager.

The subject will be allocated using the dynamic allocation method (minimization method). Details will be specified in a separate specification prepared in advance.

The results of drug concentration measurements will not be revealed until unblinding at the end of the trial.

### **3.7 Trial Procedures**

The schedule of assessments is shown in Table 3.7-1. Items that clinical trial associates are capable of performing may be performed by the clinical trial associates under the supervision of the investigator.

Table 3.7-1 Schedule of Assessments							
Assessment	Screening period (2-30 days)	Assessment period (4 weeks)					Post-treatment observation period (2 weeks)
	Screening examination	Baseline examination	Week 1 examination a (± 2 days)	Week 2 examination b (± 3 days)	Week 4 examination b (± 3 days) Withdrawal examination d	Unscheduled visit	Examination 2 weeks after the last IMP administration c (± 7 days)
Informed consent	○						
Inclusion/exclusion criteria	○	○					
Subject demographics	○						
Physical findings	○	○	○	○	○	○ e	○
Vital signs (including body weight)	○	○	○	○	○	○ e	
12-lead ECG f	○				○	○ e	
Clinical laboratory tests	○				○	○ e	
Pregnancy test g	○				○	○ e	
IGA	○	○	○	○	○		
EASI		○	○	○	○		
VAS for pruritus h		○	○	○	○		
VRS for pruritus h		○ i	← → ○				
POEM		○	○	○	○		
Affected BSA	○	○	○	○	○	○	
Treatment area		○	○	○		○	
Blood sampling for plasma drug concentration measurement			○ j		○ k		
Administration diary		○ l	← →		○		
Severity of AD		○					
Status of IMP Administration			○	○	○		
Prescription and return of IMP		○ m	○ n	○	○ o	○ n	
IMP administration		○ p	← →				

### **3.7.1 Schedule of Assessments**

#### **3.7.1.1 Screening Examination (From the Day of Obtaining Informed Consent to 2 Days Prior to the Baseline Examination)**

After acquisition of written informed consent from the subject's legal guardian, the investigator or subinvestigator will assign a subject identification code and subject number (3 digit number of site ID + S + 5 digit serial number starting from 00001).

The investigator or subinvestigator will perform the following examinations, observations, and evaluations and select subjects who meet the inclusion criteria and do not meet any of the exclusion criteria.

- Subject demographics
- Physical examination
- Vital signs (including body weight)
- 12-lead ECG (For children aged 2 - 6 years old, as much as possible. If possible, it will be conducted prior to blood sampling.)
- Clinical laboratory tests
- Pregnancy test (only for female children aged 7 - 14 years old)
- IGA
- Affected BSA
- Adverse events
- Concomitant medications and therapies

The investigator or subinvestigator will record the results of the eligibility of subjects on the list of screened subjects and the list of enrolled subjects.

##### **3.7.1.1.1 Subject Demographics**

The investigator or subinvestigator will assess or measure the following items and record them in the source document and CRF.

- Date of informed consent
- Sex
- Date of birth
- Height (Measured as an integer value in unit of centimeter. When it is measurable to one decimal place, the value is rounded to an integer value.)
- Complications
- Date of onset of AD
- Medical history (within 6 months prior to the date of informed consent)

- In- or outpatient status (outpatient)
- Subject number
- Country where the trial is conducted (Japan)
- Race
- Ethnicity
- Possibility of pregnancy

### **3.7.1.2 Subject Registration**

The investigator or subinvestigator will register all subjects in the Interactive Web Response System (IWRS).

### **3.7.1.3 Baseline Examination (2 - 30 Days After the Screening Examination)**

The investigator or subinvestigator will perform the following examinations, observations, and evaluations, and record the results in the source document and CRF.

- Physical examination
- Vital signs (including body weight)
- IGA
- EASI
- VAS for pruritus (only for 7 - 14 years of age)
- VRS for pruritus (only for 7 - 14 years of age)
- POEM
- Affected BSA
- Severity of AD
- Adverse events
- Concomitant medications and therapies

For the clinical laboratory tests and 12-lead ECG, the results of the baseline examination will be used as data for the screening examination. The investigator or subinvestigator will select subjects who meet the inclusion criteria and do not meet any of the exclusion criteria based on results of the screening and baseline examinations. Also, the investigator or subinvestigator will record the results of the subjects' eligibility on the list of screened subjects and the list of enrolled subjects.

#### **3.7.1.4 Allocation of Investigational Medicinal Products to Subjects**

The investigator or subinvestigator will enter the necessary information for subject's eligibility in the IWRS. On the day of the baseline examination, the subjects confirmed to be registered in the IWRS will be allocated to the 0.3% OPA-15406 group, the 1% OPA-15406 group, or the vehicle group. The investigator or subinvestigator will confirm the allocation result and the drug code of IMP to be prescribed for 2 weeks on the IWRS screen displaying the registration result and prescribe the IMP. The weight of the dispensed IMP will be measured (to one decimal place in unit of gram). (Hereinafter, when the weight of IMP is measured, it will be measured to one decimal place in the same manner.) After completion of all evaluations on the day of baseline examination, the first application of IMP will be given at the trial site, and date and time of the application will be recorded. The subjects will be instructed to visit the trial site without morning IMP administration on the day of the next visit.

#### **3.7.1.5 Between the Day of Baseline Examination and the Day of Week 1 Examination**

The investigator or subinvestigator will instruct the subject to evaluate the following item at  $4 \pm 2$  hours,  $8 \pm 2$  hours (if possible),  $12 \pm 2$  hours (if possible) after the first IMP administration on the day of baseline examination, and then twice daily from the next day (before IMP administration in the morning and at night) up to the morning of Week 1 examination (before administration) (up to the morning of Day 7 at the latest).

- VRS for pruritus (only for 7 - 14 years of age)

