	
(EASI), Visual Analogue Scale (VAS) for pruritus (only for 7 - 14 years of age), Verbal Rating Scale (VRS) for pruritus (only for 7 - 14 years of age), Patient-Oriented Eczema Measure (POEM), affected BSA
 
Pharmacokinetics: Blood sampling for plasma concentration of OPA-15406
 
Screening/others: Medical history, medication history, pregnancy test

Criteria for Evaluation
	
Primary Endpoint: Primary Endpoint: The number and percentage of subjects experiencing AEs
 
Secondary Endpoints: Incidence of success in IGA at Week 4, change from baseline in EASI, VAS for pruritus, VRS for pruritus, POEM, affected BSA at Week 4, and plasma concentration of OPA-15406 (trough concentration at Week 1 and Week 4)

Statistical Methods:
	
Primary Endpoint:
 
 
• The number and percentage of subjects experiencing AEs will be calculated for each treatment group
 
 
Secondary Endpoints:
 
 
• For incidence of success in IGA at Week 4, incidence of success of each treatment group and its 95% confidence interval will be calculated. The difference between vehicle group and each treatment group in the success rate and its 95% confidence interval will be calculated. Incidence of success is defined as the number of subjects whose IGA score is 0 (clear) or 1 (almost clear) and improved by at least 2 grades from baseline. Based on the Cochran-Mantel-haenszel method, the difference in success rate adjusted by the severity of IGA at baseline and its confidence interval will be calculated as primary analysis.
 
• For change from baseline in IGA at Week 1, Week 2 and Week 4, mixed-model repeated measures (MMRM) analysis with factors of treatment (0.3% or 1% OPA-15406 groups, vehicle group), timepoint, baseline IGA (mild or moderate), and interaction between treatment and timepoint will be applied with an unstructured variance covariance structure to the change from baseline up to Week 4 based on OC dataset. Kenward-Roger will be used for the calculation of standard error of fixed effects and degree of freedom. The least square mean of each treatment group will be calculated by timepoint. Also, the
 

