#### **3.7.1.6 Week 1 Examination ( $\pm 2$ Days)**

The investigator or subinvestigator will perform the following examinations, observations, and evaluations and record the results in the source document and CRF.

- Physical examination
- Vital signs (including body weight)
- IGA
- EASI
- VAS for pruritus (only for 7 - 14 years of age)
- POEM
- Affected BSA
- Blood sampling for plasma drug concentration measurement
- Adverse events

- Concomitant medications and therapies
- Status of IMP Administration

The investigator or subinvestigator will determine the treatment area (%) and enter it in the IWRS. Also, the investigator or subinvestigator will confirm the subject's allocation status on the IWRS screen and, if necessary, prescribe additional IMP. When the IMP is additionally prescribed, the weight of the dispensed IMP will be measured.

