### **3.13 Subject and Subject’s Legal Guardian Compliance**

- To avoid using drugs that are not permitted by the investigator or subinvestigator.
- To thoroughly understand the details of the administration guidance and follow it.
- To keep an administration diary every day.
- Subjects aged 7 to 14 years old should keep a pruritus diary until the morning of the Week 1 examination (Day 7 at the latest).
- When bathing or taking a shower, to administer the IMP afterwards.
- To visit the trial site on the specified visit days during the trial period.
- To visit the trial site without morning IMP administration on the day of drug concentration measurement.
- To bring the IMP, administration diary, and pruritus diary as instructed.
- To avoid excessive exercises, getting a suntan, and excessive drinking and eating and to keep regular hours to prevent possible effects on safety.
- Information obtained during participation in this trial must not be disclosed to any third party.

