6.5 Handling of Missing Values

Missing data for incidence of success in IGA will be handled as described in “[Section 6.3.1 Response in Investigator’s Global Assessment.](#)” Other variables at each timepoint will be analyzed based on the OC and LOCF data sets.

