10.1.3 Change From Baseline in Visual Analogue Scale for Pruritus

The change from baseline in visual analogue scale (VAS) for pruritus will be analyzed in the same manner as that in the overall EASI score or each EASI symptom score.

10.1.4 Change From Baseline in VRS for Pruritus up to Day 7

The change from baseline in VRS score for pruritus up to Day 7 will be analyzed in the same manner as that in overall EASI score or each EASI symptom score. Data will be collected at baseline, 4, 8, and 12 hours after the start of administration, 1 day after the start of administration (morning and night), and thereafter in the same manner up to Day 7 (morning). The same analysis will be performed by the time zone of assessment (morning or evening). Morning or evening will be determined based on the time label entered in the case report form (CRF), not using the timepoints defined in Table 6.4-2, except the baseline, which is irrespective of the time zone of assessment. Data will be collected at baseline, and the timepoints specified above on Day 1 to Day 7.

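### The itch (VRS) diary ends at the Week 1 examination, which may fall 5 or 6 days after first application, yet VRS is analysed to the morning of Day 7 (Hour 168)

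*Protocol*

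**What the plan says.** **Stop rule.** Protocol 3.7.1.5 asks for VRS ratings at about 4, 8 and 12 hours on the first day and then twice daily, "up to the morning of Week 1 examination (before administration) (up to the morning of Day 7 at the latest"). Protocol 3.13 repeats the rule: children aged 7 to 14 "keep a pruritus diary until the morning of the Week 1 examination (Day 7 at the latest"). In both places Day 7 is only a cap; the examination itself ends the diary.

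**Visit window.** Protocol 3.7.1.6 allows the Week 1 examination to be two days early or late. SAP Table 6.4-1 places Week 1 at Study Day 8. The pharmacokinetic table in SAP 11.3 makes baseline Study Day 1, so Week 1 is nominally 7 days after first application.

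**Analysis.** Protocol 7.4.2(5) and SAP 10.1.4 both plan VRS at 4, 8 and 12 hours, then morning and night from one day after the start, and "thereafter in the same manner up to Day 7 (morning"). SAP Table 6.4-2 assigns readings to windows by elapsed hours; the last is Hour 168 (162 to under 174 hours).

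**Recovery of missing readings.** VRS is not on the examination lists for Week 1 or Week 2 (protocol 3.7.1.6 and 3.7.1.7). For missing values SAP 6.5 says only: "Other variables at each timepoint will be analyzed based on the OC and LOCF data sets".

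**The concern.** A child who follows every instruction, at a site that keeps within every window, can still lack the end of the planned VRS course because the clinic visit was booked early. These gaps are created by the schedule, not by dropout or poor diary keeping.

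Three analyses are touched. The OC results at the last timepoints rest on fewer children than the earlier ones, so they are less precise, and a time course read across timepoints mixes groups of differing make-up. The LOCF results at Hour 168 include values that were not observed there. In the time-to-response analysis (SAP 10.1.9), an early-seen child without a response is censored sooner than the others.

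**Working it through.** **1. Reproduce the planned grid.** Protocol schedule: 3 readings on the first day (4, 8, 12 h), 7 mornings (1 to 7 days after the start) and 6 nights (1 to 6 days after the start): 3 + 7 + 6 = 16. SAP Table 6.4-2: Hours 4, 8 and 12, then every 12 hours from 24 to 168, that is 3 + [(168 − 24)/12 + 1] = 3 + 13 = 16. The two lists match one to one when Day 7 means 7 days after the start.

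**2. Cut the diary at an early examination.** Earliest in-window visit: 7 − 2 = 5 days after first application. The last entry, on the morning of the visit, is nominally at 24 × (visit day) hours.

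| Week 1 visit (days after start) | Last nominal entry | Timepoints collected | Timepoints lost | Age of LOCF value at Hour 168 |
|---|---|---|---|---|
| 5 | Hour 120 | 12 of 16 | 132, 144, 156, 168 | 168 − 120 = 48 h |
| 6 | Hour 144 | 14 of 16 | 156, 168 | 168 − 144 = 24 h |
| 7 to 9 | Hour 168 | 16 of 16 | none | – |

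**3. The other reading of Day 7.** If Day 7 meant Study Day 7 (6 days after the start), Hours 156 and 168 would be nominally uncollected for every child, and a child seen at 5 days would still lack the same last four.

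**4. Effect of the clock.** Windows run on elapsed hours, and on the baseline day "the first application of IMP will be given at the trial site", after all baseline evaluations. The morning entry d days after the start falls at 24d + (diary time − first-application time). Assume a 07:00 entry:
- First application at 09:00: the day 5 entry is at 120 − 2 = 118 h, in the Hour 120 window. The loss is the same four.
- First application at 14:00: the day 5 entry is at 120 − 7 = 113 h, in the Hour 108 window (102 to under 114), so Hour 120 is also empty. The day 7 entry is at 168 − 7 = 161 h, in the Hour 156 window (150 to under 162), so Hour 168 is empty even for a child seen on time.

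The shift occurs when first application is more than 6 hours later in the day than the morning entry, because 168 − 6 = 162 is the lower edge of the Hour 168 window.

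**5. Size.** Nominal coverage at Hours 132 and 144 is the share of children seen at 6 days or later; at Hours 156 and 168 it is the share seen at 7 days or later. For an OC analysis with constant residual variance and equal loss across arms, the standard error is multiplied by 1/√coverage. The documents give no visit-day distribution, so the three below are assumptions.

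| Assumed share seen at 5/6/7/8/9 days | Coverage, Hours 132–144 | SE rise | Coverage, Hours 156–168 | SE rise |
|---|---|---|---|---|
| 20/20/20/20/20% | 80% | 1/√0.80 = 1.12, 12% | 60% | 1/√0.60 = 1.29, 29% |
| 10/20/40/20/10% | 90% | 1/√0.90 = 1.05, 5% | 70% | 1/√0.70 = 1.20, 20% |
| 5/10/70/10/5% | 95% | 1/√0.95 = 1.03, 3% | 85% | 1/√0.85 = 1.08, 8% |
| nobody before 7 days | 100% | 0 | 100% | 0 |

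With 60 children and at least 8 aged 2 to 6 (protocol 3.3.1), at most 60 − 8 = 52 keep a diary, about 17 per arm if evenly split. Hour 168 then has about 17 × 0.60 = 10, 17 × 0.70 = 12 or 17 × 0.85 = 14 per arm, before any loss from the clock effect in step 4.

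**The case against.** The strongest reply is that little hangs on this. The primary endpoint is adverse events. VRS is one of several secondary measures, SAP 6.6 sets no significance level, and Hour 168 is not singled out. The same children rate itch by VAS at Weeks 1, 2 and 4. OC and LOCF are prespecified, and the MMRM uses each child's earlier 12-hourly readings, so the 1/√coverage factor does not apply to it. All of this stands and limits the stakes. It does not explain why readings that the analysis plans to use should go uncollected.

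Four stronger readings are tempting, and the documents do not support them.
- **The arms are biased against each other.** Families and investigators are blinded (protocol 3.6), so routine scheduling should affect the arms alike and each contrast stays between randomised groups. Bias could arise if visit timing followed itch, but nothing shows that it does.
- **LOCF understates the effect on itch.** That requires an effect still growing after day 5, which is an assumption.
- **Coverage is complete through Hour 120, and a full diary would fill Hour 168.** Neither is assured: the 8- and 12-hour readings are asked for only if possible, and step 4 shows afternoon starts emptying Hour 120 or Hour 168.
- **VRS is promised at Week 4 but never collected then.** The synopsis endpoint list does run "VRS for pruritus, POEM, affected BSA at Week 4", but its statistical methods make an exception for VRS, with change taken to Day 7, and protocol 7.4.2(5) and SAP 10.1.4 agree. No correction is needed on that account.

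The footnotes to Table 3.7-1 were not in the text available to me. The two body sections that state the stop rule agree with each other.

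**Conclusion.** The mismatch is real and modest. The stop rule and visit window allow a fully compliant child to finish the diary 5 or 6 days after first application, while the analysis runs to Hour 168. Nominally this costs four or two of 16 timepoints for that child. An afternoon first application can move the loss about one window earlier and can leave Hour 168 empty whatever the visit date.

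The supported consequences are lower precision in the OC results at the last timepoints and LOCF values at Hour 168 that are 24 to 48 hours old. The OC standard error rises by about 8% to 29% at Hours 156 and 168 under the assumed visit-day spreads, and not at all if nobody is seen before 7 days.

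The four and two rest on reading Day 7 as 7 days after the start, which is the reading that fills all 16 windows. The percentages rest on the assumed visit days.

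**What to change.** In protocol 3.7.1.5 and 3.13, state that every child aged 7 to 14 keeps the pruritus diary through the morning of Day 7, whatever the date of the Week 1 examination, and that children seen earlier return it at the Week 2 examination. Define Day 7 there as 7 days after first application, so that the protocol and SAP Table 6.4-2 share one clock.

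The cost is wording in the protocol and diary instructions, with no added visit. Early-seen children give up to four more one-item ratings at home, and a few diaries come back later, with some risk of loss. The change makes all 16 nominal readings collectable. It does not cure the afternoon shift, which comes from the elapsed-hour windows.
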